### 7.2.5 Visit 3: 1 Month Postsurgery ( $\pm$ 7 Days)

In France only, the following evaluations/procedures will be conducted during this visit:

- AE assessment

- Review concomitant medications
- Manifest refraction, only required if there is deterioration of 10 or more letters from baseline
- BCVA
- Goldmann applanation tonometry (study eye only)
- Measurement of undilated pupil diameter (study eye only)
- Slit-lamp biomicroscopy (study eye only)
- Dilated fundus examination (study eye only)
- Implant/sham site examination (study eye only)

In regions other than France, telephone contact will be made with the participant to determine the following:

- AE assessment
- Review concomitant medications

#### 7.2.6 Visit 4: 3 Months Postsurgery ( $\pm 14$ Days)

In France only, the following evaluations/procedures will be conducted during this visit:

- AE assessment
- Review concomitant medications
- Manifest refraction, performed if there is deterioration of 10 or more letters from baseline
- BCVA
- Goldmann applanation tonometry (study eye only)
- Measurement of undilated pupil diameter (study eye only)
- Slit-lamp biomicroscopy (study eye only)
- Dilated fundus examination (study eye only)
- Implant/sham site examination (study eye only)

In regions other than France, telephone contact will be made with the participant to determine the following:

- AE assessment
- Review concomitant medications

#### 7.2.7 Visit 5: 6 Months Postsurgery ( $\pm 30$ Days)

The following evaluations/procedures will be conducted during this visit:

- AE assessment
- Review concomitant medications
- Manifest refraction
- BCVA
- Goldmann applanation tonometry
- Measurement of undilated pupil diameter
- Slit-lamp biomicroscopy
- Microperimetry
- Dilated fundus examination
- SD-OCT
- Implant/sham site examination (study eye only)

**7.2.8 Visit 6: 12 Months Postsurgery ( $\pm$  30 Days)\***

The following evaluations/procedures will be conducted during this visit:

- AE assessment
- Review concomitant medications
- NEI-VFQ-25
- Reading speed
- Manifest refraction
- BCVA
- Goldmann applanation tonometry
- Measurement of undilated pupil diameter
- Slit-lamp biomicroscopy
- Microperimetry
- Dilated fundus examination
- SD-OCT
- Implant/sham site examination (study eye only)

**7.2.9 Visit 7: 16 Months Postsurgery ( $\pm$  30 Days)\***

The following evaluations/procedures will be conducted during this visit:

- AE assessment
- Review concomitant medications
- Manifest refraction
- BCVA
- Goldmann applanation tonometry
- Measurement of undilated pupil diameter
- Slit-lamp biomicroscopy
- Microperimetry
- Dilated fundus examination
- SD-OCT
- Implant/sham site examination (study eye only)

**7.2.10 Visit 8: 20 Months Postsurgery ( $\pm$  30 Days)\***

The following evaluations/procedures will be conducted during this visit:

- AE assessment
- Review concomitant medications
- Manifest refraction
- BCVA
- Goldmann applanation tonometry
- Measurement of undilated pupil diameter
- Slit-lamp biomicroscopy
- Microperimetry
- Dilated fundus examination
- SD-OCT
- Implant/sham site examination (study eye only)

**7.2.11 Visit 9: 24 Months Postsurgery ( $\pm$  30 Days)**

Participants who have a Month-24 study visit scheduled after 01 December 2021 will complete the visit and exit from the study at the M24 visit.

The following evaluations/procedures will be conducted during this visit:

- AE assessment
- Review concomitant medications
- NEI-VFQ-25
- Reading speed
- Manifest refraction
- BCVA
- Goldmann applanation tonometry
- Measurement of undilated pupil diameter
- Slit-lamp biomicroscopy
- Microperimetry
- Dilated fundus examination
- SD-OCT
- Fundus autofluorescence imaging
- Color digital fundus photography
- Implant/sham site examination (study eye only)

**7.2.12 Visit 10: 36 Months Postsurgery ( $\pm$  30 Days)**

Participants who have completed the Month 24 visit and have a Month-36 study visit scheduled before 01 December 2021 will complete the visit and exit from the study at the Month-36 study visit. Participants who have completed the Month 24 visit and have a Month-36 study visit scheduled after 01 December 2021 will not complete this visit. These subjects will complete a safety check-in call and exit the study by 01 December 2021.

The following evaluations/procedures will be conducted during this visit:

- AE assessment
- Review concomitant medications
- NEI-VFQ-25
- Reading speed
- Manifest refraction
- BCVA
- Goldmann applanation tonometry
- Measurement of undilated pupil diameter
- Slit-lamp biomicroscopy
- Microperimetry
- Dilated fundus examination
- SD-OCT
- Implant/sham site examination (study eye only)

**7.2.13 Visit 11: 48 Months Postsurgery ( $\pm$  30 Days)**

Participants who have completed the Month-24 and Month-36 visits and have a Month-48 study visit scheduled before 01 December 2021 will complete the visit and exit from the study at the Month-48 study visit.

Participants who have completed the Month-24 and Month-36 visits and have a Month-48 study visit scheduled

after 01 December 2021 will not complete this visit. These subjects will complete a safety check-in call and exit the study by 01 December 2021.

The following evaluations/procedures will be conducted during this visit:

- AE assessment
- Review concomitant medications
- NEI-VFQ-25
- Reading speed
- Manifest refraction
- BCVA
- Goldmann applanation tonometry
- Measurement of undilated pupil diameter
- Slit-lamp biomicroscopy
- Microperimetry
- Dilated fundus examination
- SD-OCT
- Implant/sham site examination (study eye only)

\*During the COVID-19 pandemic, the acceptable visit window is extended to +119 Days from the original scheduled visit for Month 12, 16, 20, and 24 visits, as described in Section 6.1.

### 7.3 CLINICAL LABORATORY TESTS

All premenopausal female participants will undergo a urine pregnancy test at the screening visit.

### 7.4 PROTOCOL DEVIATIONS

Protocol deviations will be reported to the sponsor as they are discovered.

## 8. INVESTIGATIONAL PRODUCT MANAGEMENT

### 8.1 DESCRIPTION

#### 8.1.1 Formulation

The study device is the NT-501 implant, NT501.6A.02 encapsulated cell therapy (ECT), delivering a nominal CNTF dose of 20 ng/device/day.

#### 8.1.2 Storage

Storage of the shipping container is at room temperature, which is not to exceed 55°C (131°F) or fall below –20°C (–4°F) and must be used within the “use by” date. Storage of the box at temperatures outside this range could result in the internal temperature of the box and the implant exceeding the allowable range of 16°C to 37°C. If a planned implant surgical procedure is delayed such that the shipped investigational product will be in the shipping container for a period beyond the identified “use by” date, then Neurotech Pharmaceuticals Inc. must be notified and an alternate/replacement shipment will be provided.

## 8.2 PACKAGING AND SHIPMENT

The NT-501 device is contained within the primary packaging, which is comprised of a sealed clear plastic container that contains the transport medium. The NT-501 device is suspended within the transport medium by a titanium clamp which, in turn, is held in position by a luer cap that is twisted onto the flange of the primary packaging. The inner surfaces of the primary packaging, the transport medium, and all other component surfaces are sterile. In addition, as long as the secondary packaging remains sealed, the exterior of the primary packaging within the secondary packaging is maintained sterile. Product labeling is located on the exterior, nonsterile side of the secondary packaging seal. This container is protected in an insulated transport carton.

## 8.3 DOSE AND ADMINISTRATION

The study device is the NT-501 implant, NT501.6A.02 ECT (delivering a nominal CNTF dose of 20 ng/device/day), which will be implanted per randomization and will remain in situ for the duration of the study. There are no plans to remove the device, except in the case of participant intolerance or complications such as infection or inflammation.

## 8.4 ACCOUNTABILITY

All investigational product and supplies provided by the sponsor and used during this study must be maintained in a secure location. The investigator has overall responsibility for ensuring that the investigational product is stored in a safe, limited-access location under the specified appropriate storage conditions. Limited responsibility may be delegated to an unmasked nominated representative, but this delegation must be documented.

The investigator agrees not to supply any NT-501 device to any person not enrolled in this study or to any person not delegated to perform investigational product handling.

The investigator/recipient will acknowledge receipt of the investigational product, indicating shipment content and condition. A record of the TempTale® readings must be kept for each shipment. Damaged supplies will be reported to the sponsor. Accurate records will be kept for all investigational products supplied and received. The date of implantation will be recorded.

Investigational product will not be returned to the sponsor except in an instance of device inspection failure where the sponsor requests that the failed device or a portion thereof should be returned for investigation.

All investigational product not implanted per protocol into enrolled study participants must be destroyed on site as dictated by the appropriate biohazardous waste standard operating or study specific procedure at the participating institution (if appropriate). Investigational products should only be destroyed after investigational product accountability has been performed and all investigational products are accounted for. Duplicate devices provided at the time of surgery that are not required for implantation should be marked in large letters “NOT FOR HUMAN USE” following successful implantation of the original device until the time of destruction.

## 9. CONCOMITANT MEDICATIONS

Any concomitant medications a participant is receiving at the start of the study or given for any reason during the study (except for routine medications given for ocular procedures required by the protocol, such as a topical anesthetic), including over the counter, supplements and herbal formulas, must be recorded in the source document, including start and stop dates, dosing, route of administration, and indication information. Recording of concomitant medications on the case report forms (CRFs) must be done according to the instructions

provided in the study regulatory binder. In addition, all ocular and non-ocular procedures (excluding study surgery and procedures) must also be recorded in the source document, including start and stop dates. Recording of procedures on the CRFs must be done according to the instructions provided in the study regulatory binder.

## 9.1 PROHIBITED CONCOMITANT THERAPY

Ocular administration of subconjunctival or intravitreal antibiotics is prohibited unless treating a sight-threatening condition. The ocular administration of gentamicin or other aminoglycosides topically, peri-ocularly, or by injection is prohibited unless treating a sight-threatening condition for which no other alternatives are appropriate. Systemic administration of aminoglycosides should also be avoided. Aminoglycosides are known to be toxic to RPE cells and ocular administration could harm the cells in the NT-501 device.

## 10. ADVERSE EVENTS

An AE is any untoward medical occurrence in humans, whether or not considered treatment- or procedure-related, which occurs during the conduct of a clinical trial. Any change in clinical status, ophthalmological assessments, etc., that is considered clinically significant by the study investigator and requires intervention is considered an AE. Medical conditions or diseases present before a participant starts study treatment are only considered AEs if they worsen after the participant starts study treatment (temporal association).

A suspected adverse reaction (related AE) is any event for which there is a reasonable possibility that the treatment caused the AE. A reasonable possibility implies that there is evidence that the treatment caused the event.

### 10.1 DOCUMENTING ADVERSE EVENTS

All AEs, either observed by the investigator or their medical collaborators, or reported by the participant spontaneously, or in response to direct questioning, will be reported. Any AE regardless of severity or potential association with the NT-501 device, CNTF, or the study procedures must be documented in study records by the investigator and appropriately reported.

All AEs will be reported within the participant's records and in the EDC system. All AEs should be entered into the data system as soon as possible after identification by the site personnel. All AEs will be recorded from the time of surgery until the last study visit.

### 10.2 ASSESSMENT OF INTENSITY

#### Guidelines for Assessing Intensity of an Adverse Event

The investigator should use the following definitions when assessing intensity of an AE:

- **MILD:** Transient (< 48 hours) or mild discomforts, no or minimal medical therapy or intervention required, hospitalization not necessary, no or little limitation in normal activities
- **MODERATE:** Mild to moderate limitation in activity, some assistance may be needed; possibly none but usually minimal intervention/therapy required; hospitalization possible
- **SEVERE:** Marked limitation in activity, some assistance usually required; medical intervention/therapy required; hospitalization possible or likely

- **LIFE-THREATENING:** Extreme limitation in activity, significant and immediate assistance required; significant medical/therapy intervention required to prevent loss of life; hospitalization, emergency treatment, or hospice care probable
- **FATAL:** Death

### 10.3 ASSESSMENT OF CAUSALITY

#### Guidelines for Determining Causality of an Adverse Event

The investigator will answer the following question when assessing causality of an AE to study treatment: “Is there a reasonable possibility that the treatment caused the event?” A reasonable possibility implies there is evidence that the specific event was caused by the study treatment. An affirmative answer designates the event as a suspected adverse reaction, and the AE is therefore considered “related.” If the answer is no, then the AE is considered “unrelated.” For every related AE, the investigator will determine the causality in relation to the surgical procedure, to the device itself, and to CNTF.

Regarding relatedness of AEs, there are 3 possibilities. These include the following:

- **Related to surgical procedure:**  
Ocular events that occur immediately following the surgical procedure or later if they are directly related to the procedure
- **Related to the device itself:**  
These would include malposition of the device with impingement of the participant’s visual field, inflammation of the vitreous, or visible deterioration of the device on inspection via the ophthalmoscope
- **Related to CNTF:**  
The known events related to CNTF release in the eye are clearly listed in the reference safety information of the investigator’s brochure

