### 11.3 NOTIFYING FDA/REGULATORY AUTHORITIES

After the SAE has been reported by the principal investigator and assessed by the IND sponsor, the IND sponsor or their designee must report the event to the appropriate regulatory authorities using 1 of these 2 options:

- Standard reporting (report in the annual report). This option applies if the AE is classified as one of the following:
  - Serious, expected, suspected adverse reaction (serious, expected, and related)
  - Serious and not a suspected adverse reaction (serious and not related)
- Expedited reporting. This option applies if the AE is classified as SUSAR (serious, unexpected, and related).

The sponsor must report an AE as a suspected adverse reaction (related AE) only if there is evidence to suggest a causal relationship between the study treatment and the AE, such as:

- A single occurrence of an event that is uncommon and known to be strongly associated with study treatment
- One or more occurrences of an event that is not commonly associated with study treatment, but is otherwise uncommon in the population exposed to the study treatment
- Aggregate analysis of specific SAEs observed in a clinical trial (such as known consequences of the underlying disease or condition under investigation or other events that commonly occur in the study population independent of study treatment) that indicates those events occur more frequently in the study treatment group than in a concurrent or historical control group

- Any findings from clinical or epidemiological studies, analysis of data pooled across multiple studies, published or unpublished scientific papers, or from animal or in vitro testing that would result in a safety-related change in the protocol, informed consent, general investigational plan section of the IND, or other aspects of the overall conduct of the trial

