**Delayed Dark Adaptation:** This AE has only been reported in study participants with MacTel with 11 cases out of the 55 (22%) implanted eyes in the Phase 1 and 2 studies. In the studies of participants with RP and atrophic AMD, this AE was not reported. The cause of the delayed dark adaptation is not well understood, but a plausible explanation is that it is related to either miosis and/or the observed effect on photoreceptors following treatment with CNTF. CNTF treatment results in a change in rod photoreceptor nucleus phenotype, featuring an increase in euchromatin and an increase in nuclear size. Chronic stimulation of retinal cells with CNTF has been shown to affect gene expression in photoreceptors including reduction of phototransduction genes such as rhodopsin in animal models. As rod photoreceptors are more light sensitive than cone cells and are almost entirely responsible for night vision, it is possible that the CNTF-mediated changes in the rod photoreceptors may affect the participant's ability to adapt to the dark. The reason why this AE is limited to a small subpopulation of the participants with MacTel is not well understood.

An increase in retinal thickness is observed in the majority of all eyes treated with CNTF at the dose proposed for study in Phase 3. Taken together, the preclinical data in dogs and the fact that macular thickening is seen only in the treated eyes, suggest that the AE of delayed dark adaptation may well be a direct consequence of CNTF treatment.

There are risks associated with the diagnostic procedures required for participants in this study. However, these are standard procedures that are performed as part of a normal eye and medical examination. Some of the discomforts associated with the ocular examination include the following:

- Dilating drops or anesthetic drops may sting. They can cause an allergic reaction, or if contaminated, can cause an infection, but neither of these problems is very likely to occur.
- Dilating drops can also cause a sudden increase of pressure (acute glaucoma) in eyes that are already predisposed to develop this condition. There is little risk of glaucoma being triggered in this way, but if it is, treatment is available.
- In rare instances, the cornea may be abraded during measurement of IOP or the use of a contact lens (used for examination purpose only and not a contact lens used to correct a participant's refractive error).

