There are risks associated with the procedures required for participants in this study. The fluorescein angiogram requires injection of dye in the participant's arm. Local subcutaneous infiltration of dye may create discomfort and temporary staining of the skin (< 5% risk). There is a chance of fainting, ecchymosis at the site of injection, and a remote possibility of cellulitis from the needle track. After the dye injection, some participants (< 5%) may experience nausea that usually passes after a few seconds, and rarely, participants vomit.

Allergic reactions to fluorescein are uncommon; reactions may cause hives and itching. These reactions are usually treated with oral or injectable antihistamines as needed. Anaphylaxis from fluorescein is extremely rare and may be life-threatening. Fluorescein dye routinely causes a yellowing/orange color to the skin and urine that generally passes in 24 hours.

Imaging using OCT is an FDA-approved technique, which is not associated with any AEs.

Fundus photography and autofluorescence are not associated with any AEs, although some participants may experience mild discomfort due to the bright lights.

There are also risks associated with the operations to implant and explant the device and with the sham procedure. In general, the risks of intraocular surgery are very small. Some side effects could occur locally in the eye and could affect the participant's vision. There may be pain or infection, a small amount of bleeding, miosis, retinal detachment, cataract, vitritis, and/or mild astigmatism. In many cases, topical antibiotics and topical steroids can treat minor degrees of inflammation or infection. More serious infection or inflammation may require further surgery on the eye, likely with removal of the implant. The sham procedure of subconjunctival injection of lidocaine and inserting a final suture in the conjunctiva may be accompanied by subconjunctival bleeding, pain, or infection, all of which can be readily treated without any functional changes or any other permanent structural changes.

The risks of the sham procedure include: the risk of pre-operative sedation, the risk of the local anesthetic, and the risk of the superficial conjunctival incision and suture.

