10.1 Treatment-Emergent Adverse Events (TEAEs)

The collection period of adverse events, serious and non-serious, will begin after surgery and continue throughout the course of the participant's participation in the study. For analysis purposes, all adverse events will be classified as TEAE.

The TEAEs will be presented by treatment group (NT-501 implant versus sham). Summaries for TEAEs include the following: all TEAEs regardless of causality, treatment-related TEAEs, ocular TEAEs, treatment-related ocular TEAEs, TEAEs by intensity, serious adverse events (SAEs), and TEAEs leading to discontinuation from the study.

All TEAEs will be coded using the Medical Dictionary for Regulatory Activities (MedDRA).

The incidence of TEAEs will be summarized for each treatment group by system organ class and preferred term. If a subject reports the same AE more than once, then that subject will only be counted once in the summary of that AE, using the most severe intensity.

AEs will be summarized through Month 24 and through the end of the trial/Month 48:

- All ocular TEAEs;
- All non-ocular TEAEs;
- All ocular TEAEs by intensity;
- All non-ocular TEAEs by intensity;
- All ocular TEAEs by relationship to surgical procedure/device/CNTF;
- All non-ocular TEAEs by relationship to surgical procedure/device/CNTF;
- Ocular SAEs;
- Non-ocular SAEs;
- Ocular SAEs by relationship to surgical procedure/device/CNTF;
- Non-ocular SAEs by relationship to surgical procedure/device/CNTF;
- Deaths; and
- Ocular/Non-ocular TEAEs that led to explantation of IP.

All SAEs and TEAEs leading to premature withdrawal from the study will be listed.

Summaries will be presented using frequency counts and percentages (i.e., the number and percentage of study eyes/participants with an event as well as the total number of events). Study eyes/participants with multiple occurrences of the same AE or a continuing AE will be counted once, and only the maximum severity level will be presented in the severity summaries, and the worst/highest relationship level in the relationship summaries. A separate table will summarize all TEAEs when each of them is considered unique, hereafter referred as AE count table. In addition, a listing containing individual participant adverse event data for all deaths and serious adverse events will be provided, separately. All adverse events will be presented in individual subject data listings.

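### Protocol 10.3 limits procedure-related adverse events to ocular events, although the SAP tabulates non-ocular events by relationship to the procedure

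*Protocol*

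**What the plan says.** Protocol 10.3, headed as guidelines, works in two steps. The investigator first answers a general question: "Is there a reasonable possibility that the treatment caused the event". A yes makes the event related. For every related event the investigator then judges causality against the surgical procedure, the device and CNTF. The section continues: "Regarding relatedness of AEs, there are 3 possibilities". The three items are worded differently:

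- **Procedure:** "Ocular events that occur immediately following the surgical procedure or later if they are directly related to the procedure".
- **Device:** an open set of examples, including malposition, vitreous inflammation and visible deterioration of the device.
- **CNTF:** "The known events related to CNTF release in the eye are clearly listed in the reference safety information" of the investigator's brochure. No criterion is given for an event that is not listed.

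Protocol 13 includes among the sham risks "the risk of pre-operative sedation, the risk of the local anesthetic". Protocol 1.1 says that the implant surgery is also done under local anesthetic.

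SAP 10.1 plans "All non-ocular TEAEs by relationship to surgical procedure/device/CNTF", with a matching table for non-ocular serious events. Appendix C lists both. SAP 10.1 also counts a participant once in the relationship summaries, at the highest relationship level.

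**The concern.** The procedure item excludes a class of events that the SAP sets out to tabulate. If sites follow the item as written, the procedure entries in the non-ocular tables stay empty in both arms. If some sites follow it and others follow the broader duty to judge every related event, the entries mix two rules. Either way, a reader of the study report could not tell whether a zero means that no reactions occurred or that the definition allowed none.

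Separating procedure, device and CNTF effects is a stated safety aim in Protocol 4.1.2 and SAP 4.4.2. The implant arm is exposed to all three sources and the sham arm only to a procedure, so the split helps to interpret differences in event rates between arms.

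**Working it through.** No sample size, error rate or event count enters this point, so the check sets the texts side by side.

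1. **Trace one event through 10.3.** Take a non-ocular reaction to the local anesthetic, in either arm.
   - Opening question: yes, so the event is related.
   - Duty to judge all three sources: applies, because it covers every related event.
   - Procedure item: no match, because it names ocular events only.
   - Device item: none of the examples resembles it.
   - CNTF item: it points to known effects of CNTF release in the eye, so no match.
   - Result: a related event for which none of the three descriptions fits. An investigator who marks it as procedure-related departs from the wording of that item; one who keeps to the wording leaves the source blank.

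2. **Compare with Protocol 13.** Sedation and local anesthetic are named as risks of the sham procedure. The protocol therefore recognizes causes within the procedure whose effects need not be ocular.

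3. **Compare with SAP 10.1 and Appendix C.** Both plan non-ocular tables with the procedure as one of the sources. Under the literal procedure item, those entries would be zero in each arm whatever happened.

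4. **Follow the same event through the other summaries.** Protocol 10.1 requires every event to be recorded whatever its possible association. The event therefore appears in the non-ocular totals and, if serious, in the non-ocular serious totals. It also appears in the treatment-related summary, because relatedness comes from the opening question. Only the split by source loses it.

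5. **Check whether the SAP counting rule resolves sources.** It does not. Highest relationship level has a meaning when levels are ordered, but procedure, device and CNTF are sources with no stated order. The question arises in practice: 10.3 gives vitreous inflammation as a device example, while Protocol 13 lists vitritis among the side effects of the operations. Protocol 13 also lists miosis there, and elsewhere attributes it to CNTF. Section 10.3 does not say outright that more than one source may be marked.

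6. **Size.** The documents give no rate of non-ocular procedure reactions, so the number that might be misplaced cannot be derived.

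**The case against.** The strongest reply is that 10.3 is guidance. Its heading says so, the device item is plainly illustrative, and the duty to judge every related event against all three sources is not limited to ocular events. Protocol 4.1.2 likewise rests attribution on what the investigator believes. A sensible investigator could mark a sedation reaction as procedure-related, and nothing forbids marking two sources. This stands as far as it goes. It means that under-attribution is possible but not established, and that the priority is low. It does not remove the conflict, because the only description of a procedure-related event still says ocular.

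Three stronger readings are tempting, and the documents do not support them.

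- **CNTF-related events are by construction already listed ones.** A reader might infer this from the CNTF item. The item says only where known effects are listed; it has no limiting word. The opening question and the three-source duty both let a new effect be attributed to CNTF. The fair criticism is that an unlisted effect gets no criterion, which may steer attribution toward the list.
- **Expedited reporting is weakened.** Under Protocol 11.2 and 11.3 it depends on an event being serious, related and unexpected. The source marked plays no part, and the sponsor or its designee makes the final decision. Section 11.3 also accepts, as possible evidence of causality, "One or more occurrences of an event that is not commonly associated with study treatment" if it is otherwise uncommon in the exposed population.
- **Delayed dark adaptation shows how many events would be lost.** Protocol 13 says of it: "This AE has only been reported in study participants with MacTel with 11 cases out of the 55 (22%) implanted eyes". (11/55 is 20%, not 22%, but that is a separate matter.) Applying that rate to a hypothetical new effect, and assuming that none would be attributed to CNTF, has no basis in the documents. The example points the other way: Protocol 13 goes on to suggest that the effect may well be due to CNTF, and Appendix C tabulates it by arm whatever its attribution.

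**Conclusion.** The conflict is real and narrow. The procedure item in Protocol 10.3 omits non-ocular events. It disagrees with the three-source duty in the same section, with the sedation and anesthetic risks in Protocol 13, and with the non-ocular relationship tables in SAP 10.1 and Appendix C. Non-ocular procedure reactions have no matching definition and may be under-attributed in those tables.

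Severity is low. The affected tables are descriptive. Total adverse event and serious adverse event counts, treatment-related totals, expedited reporting and all efficacy analyses are unchanged.

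The conclusion assumes that at least some investigators apply the wording of 10.3 literally, and that the case report form or its guidance, which cannot be seen here, does not already correct it.

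**What to change.** In Protocol 10.3 (and any matching case report form guidance):

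- Extend the procedure item to ocular or non-ocular events caused by the implant or sham procedure, including sedation and anesthesia.
- State that procedure, device and CNTF are each judged yes or no for every related event, and that more than one may be yes.
- State that the CNTF effects listed in the reference safety information are examples and not an exhaustive list.

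In SAP 10.1, replace the highest-level counting rule for source with separate tabulations of procedure, device and CNTF attribution, counting a participant under each that applies. Appendix C should follow.

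The cost is a few sentences in each document, and no new assessments are needed. The SAP preface allows amendments up to database lock. The small downside is that related events already recorded may need a query to the site to confirm their source, ideally before lock and without reference to the comparison between arms.
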